7 ADVERSE EVENTS AND SAFETY REPORTING

7.1 Safety and Tolerability Assessments

Safety and tolerability will be assessed on an ongoing basis by review of reported AEs, physical examinations, 12-lead ECGs, vital signs (including weight, seated SBP/DBP, heart rate, and temperature), and clinical safety labs (hematology, serum chemistry, and urinalysis).

7.2 Definition of Adverse Event

An AE is defined in 21 CFR 312.32(a) as follows:

Any untoward medical occurrence associated with the use of a drug in humans, whether or not considered drug related.

An AE (also referred to as an adverse experience) can be any unfavorable and unintended sign (e.g., an abnormal laboratory finding), symptom, or disease temporally associated with the use of a drug, and does not imply any judgment about causality. An AE can arise with any use of the drug (e.g., off-label use, use in combination with another drug) and with any route of administration, formulation, or dose, including an overdose.

AEs will be regarded as “pretreatment” if they occur during the placebo washout period or placebo run-in period. TEAEs are defined as any AE that starts or increases in severity after the first randomized dose of study treatment (active or placebo) on Day 4.

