2.2 Secondary Objectives

- To compare pre-treatment (Day 3) to end of treatment (Day 8) mean daytime CGM glucose for single and multiple doses of ORMD-0801 vs placebo.
- To compare pre-treatment (Day 3) to end of treatment (Day 8) mean nighttime CGM glucose for single and multiple doses of ORMD-0801 vs placebo.
- To compare pre-treatment (Day 3) to post-treatment washout (Day 9) 24-hour CGM glucose for single and multiple doses of ORMD-0801 vs placebo.
- To compare post-prandial glucose measurements for single and multiple doses of ORMD-0801 vs placebo.
- To compare pre-treatment (Day 3) to end of treatment (Day 8) insulin pharmacokinetics (PK) for single and multiple doses of ORMD-0801 vs placebo.
- To compare pre-treatment (Day 3) to end of treatment (Day 8) C-peptide pharmacodynamics (PD) for single and multiple doses of ORMD-0801 vs placebo.
- To compare defined events of hypoglycemia for single and multiple doses of ORMD-0801 vs placebo.

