3 INVESTIGATIONAL PLAN

3.1 Overall Study Design and Plan

This study will enroll approximately 30 adult subjects with T2DM from age 20 to 75 inclusive. Following a 7-10 day Screening period, eligible subjects will enter a 3-day single-blind placebo run-in. On Day 4, each subject will be randomized to a treatment sequence that will include three treatment assignments for each of three treatment Periods according to the randomization scheme. All subjects will receive placebo plus two of the following: ORMD-0801 460 IU **qd**, ORMD-0801 **bid**, or ORMD-0801 **tid**. Subjects will receive the randomized treatment from Day

4 through Day 8. A 24-hour single-blind placebo washout will be done on Day 9. For all treatment Periods, pre-treatment CGM data will be collected for approximately 36 hours prior to treatment (Days 1-3). The cannula will be changed and the monitor will remain in place throughout the 5-day treatment period (Days 4-8) and for an additional 24 hours post-treatment (Day 9). Blood samples for PD analysis will be taken pre-treatment (Day 3) and at end of treatment (Day 8) to check for concentrations of insulin and C-peptide in the blood. In addition, adverse events, clinical laboratory values, vital signs, and electrocardiograms (ECGs) will be evaluated periodically for safety. Subjects will be discharged on the morning of Day 10. Each treatment Period will be separated by a 2-week washout. A final follow-up visit will be performed 1 week after the end of the third treatment period.

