5.3.1.1 Single-Blind Placebo Administration

Placebo will be administered during Visit 2 on Days 1, 2, 3, and 9. On Day 1, subjects will receive one dose of placebo in the morning, followed by breakfast at least 45 minutes later. They will receive 4 additional doses of placebo to take one dose at least 45 minutes before lunch, one dose at bedtime, one dose at least 45 minutes before breakfast on Day 2, and one dose at least 45 minutes before lunch on Day 2. Subjects will be provided with an evening dose of placebo at approximately 10 pm (\pm 60 minutes) on Day 2. On Days 3 and 9, subjects will receive a dose of

single-blind placebo at approximately 7am (\pm 60 minutes), approximately 1pm (\pm 60 minutes), and before bed at approximately 10 pm (\pm 60 minutes).

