5.3.1.2 Double-Blind Treatment Administration

Study treatment (active or placebo) will be administered during Visit 2 on Days 4-8. **Prior to administering the scheduled dose of study drug, the most recent available reading on the CGM monitor must indicate a blood glucose of ≥ 70 mg/dL.** On all days, subjects will receive a dose of study treatment or placebo at approximately 7am (\pm 60 minutes), approximately 1pm (\pm 60 minutes), and a dose before bed at approximately 10 pm (\pm 60 minutes).

Subjects may be randomized to receive ORMD-0801 qd, bid, or tid:

- Subjects receiving ORMD-0801 qd will receive their dose at approximately 10pm (\pm 60 minutes), while receiving identical placebo at approximately 7am (\pm 60 minutes) and at approximately 1pm (\pm 60 minutes).
- Subjects receiving ORMD-0801 bid will receive their doses at approximately 7am (\pm 30 minutes) and before bed at approximately 10pm (\pm 60 minutes), while receiving placebo at approximately 1pm (\pm 60 minutes).
- Subjects receiving ORMD-0801 tid will receive their doses at approximately 7am (\pm 60 minutes), at approximately 1pm (\pm 60 minutes), and before bed at approximately 10pm (\pm 60 minutes).

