8.4.2 Adverse Events

AEs will be coded using the most current version of MedDRA. The severity of AEs will be graded according to NCI CTCAE version 4.03. AEs will be regarded as “pretreatment” if they occur during the placebo washout period or placebo run-in period. TEAEs are defined as any AE that starts or increases in severity after the first randomized dose of study treatment on Visit 2/Day 4.

The incidence of TEAEs will be tabulated by MedDRA preferred term, system organ class, treatment group, severity, and assigned relationship to study treatment. The incidence for each TEAE will be provided as the total number of subjects that experienced the TEAE, as well as the percentage of the population that this represents. If a TEAE is reported more than once for a

given subject, the greatest severity and the worst-case attribution will be presented in the summary tables.

TEAEs will be listed for individual subjects, along with information regarding onset and end dates, onset time where available, severity, seriousness, relationship to study treatment, action taken, and outcome. A similar listing will be prepared for the pretreatment AEs.

Pretreatment AEs and TEAEs that lead to withdrawal from the study will be separately listed and summarized. Similarly, separate tabulations and listings will be prepared for pretreatment and treatment-emergent SAEs.

Descriptive statistics will be generated as appropriate (i.e., frequency for categorical data). Inferential statistical analysis comparing the AE data between active and placebo is not planned.

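### Minor: the pretreatment AE definition takes in Day 9, which follows randomised dosing, and SAP 2.13 dates incomplete AE onsets from a single first dose in a three-period crossover

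*Protocol*

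**What the plan says.** **Classification.** Protocol 7.2 and 8.4.2 use the same words: AEs are pretreatment "if they occur during the placebo washout period or placebo run-in period". Protocol 8.4.2 continues: "TEAEs are defined as any AE that starts or increases in severity after the first randomized dose of study treatment on Visit 2/Day 4". Protocol 7.2 has an equivalent sentence. SAP 2.7.1 repeats the TEAE definition and has no pretreatment class.

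**Schedule.** Protocol 3.1 states: "A 24-hour single-blind placebo washout will be done on Day 9". Protocol 5.3.1.1 states: "Placebo will be administered during Visit 2 on Days 1, 2, 3, and 9". Randomised dosing runs from Day 4 to Day 8. No placebo dosing is described for the two-week gap between periods. One secondary objective in Protocol 2.2 reads: "To compare pre-treatment (Day 3) to post-treatment washout (Day 9) 24-hour CGM glucose", so the Protocol itself places Day 9 after treatment.

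**Outputs.** After the TEAE listing, Protocol 8.4.2 adds: "A similar listing will be prepared for the pretreatment AEs". For serious events, "separate tabulations and listings will be prepared for pretreatment and treatment-emergent SAEs". SAP 4.1 lists an overall AE summary (14.3.1.1) and four treatment-emergent tables (14.3.1.2 to 14.3.1.5). SAP 3.1 lists one AE listing (16.2.7.1).

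**Partial dates.** SAP 2.13 refers to one first dose date for the whole study. If the day is missing, the onset is set to the first dose day when month and year match, and otherwise to the 1st of the month. If the month is missing and the year matches, the onset is set to the first dose date.

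**Two labels.** Protocol 7.4 starts AE monitoring after the first *washout period placebo*. Protocol 7.4.1 gives the CRU-housed days as *Day 1-2*.

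**The concern.** A classification rule should send each event to one place. Here two adjacent sentences send a new Day 9 event to two. The TEAE sentence is tied to the first randomised dose and not to each period, so a new event in the run-in of Period 2 or 3 also meets both definitions.

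Day 9 is not remote from exposure. Protocol 5.3.1.2 says: "Subjects receiving ORMD-0801 qd will receive their dose at approximately 10pm", and the bid and tid regimens also include the 10pm dose. The first Day 9 placebo, at 7am, is therefore nominally 9 hours after an active dose in all three ORMD-0801 regimens (7 to 11 hours with both ±60-minute windows). That does not decide the classification, but it shows why Day 9 events should not be set aside as pretreatment.

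The date rule raises a related problem. Regimens change on Day 4 of each period, so one study-level anchor can move an incompletely dated event out of the period in which it occurred.

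Protocol 2.1 makes safety a primary objective; Protocol 8.1 calls it a secondary endpoint assessed mainly on AEs. Either way, AE counts by regimen are a main product of the trial.

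**Working it through.** **1. Calendar.** Inputs: 10-day periods, two washouts of 14 days (the stated minimum, assumed exact) and 7 days to follow-up (Protocol 3.3 and 3.4). 3 × 10 + 2 × 14 + 7 = 65, which reproduces the Protocol's figure of about 65 days. Periods start on study days 1, 25 and 49; Day 4 falls on study days 4, 28 and 52.

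**2. Days meeting both definitions.** Run-in Days 1-3 plus Day 9 give 4 × 3 = 12 pretreatment days: 1-3, 9, 25-27, 33, 49-51 and 57. A new AE after the first randomised dose on study day 4 is a TEAE. Only days 1-3 escape, so 12 − 3 = 9 days meet both rules:
- Day 9 of each period: study days 9, 33 and 57.
- Run-in of Periods 2 and 3: study days 25-27 and 49-51.

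**3. Day missing.** Assume that the imputed date assigns the event to the most recent Day 4. Let k be the days from that period's Day 4 to the true onset. The imputed date stays on or after Day 4 only if the 1st of a month lies between Day 4 and onset inclusive. Over 365 start dates this happens 12 × (k + 1) times. Period 2 onsets in the same month as the first dose are set to a Period 1 date, and are already among the failures.

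| True onset | k | Kept in period | Combinations | Dated before Day 4 |
|---|---|---|---|---|
| Days 4-10, Period 2 or 3 | 0 to 6 | 12 × (1 + … + 7) = 336 | 365 × 7 = 2,555 | 2,219 (86.8%) |
| 14-day outpatient interval after Period 2 | 7 to 20 | 12 × (8 + … + 21) = 12 × 203 = 2,436 | 365 × 14 = 5,110 | 2,674 (52.3%) |

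The rows for Periods 2 and 3 are the same whether first dose means Day 1 placebo or Day 4. For the interval after Period 1 it matters. If first dose means Day 4, the imputed date is Day 4 or a later 1st of the month, so nothing moves. If it means Day 1, the 52.3% applies there too. Period 3 is followed by only 7 to 9 days to follow-up, so the 14-day row does not apply to it.

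**4. Month missing.** When the year matches, every Period 2 or 3 event goes to the first dose date in Period 1.

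**5. Example.** Period 1 Day 1 = 10 March, so Period 1 Day 4 = 13 March and Period 2 Day 4 = 6 April (24 days later). An 8 April event with the day missing is dated 1 April, in the washout after Period 1. With the month missing it is dated 13 March, if first dose means Day 4.

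**6. CRU label.** Evening of Day 2 to morning of Day 10 is 10 − 2 = 8 nights, which matches the Synopsis. *Day 1-2* covers a day with no overnight stay and only the first of those nights.

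**The case against.** The best defence is that *placebo washout period* does not mean Day 9. Protocol 7.4 uses the same vocabulary for a dose that, by the schedule, can only be the Day 1 run-in placebo. On that reading Protocol 7.2 names one pre-dose phase twice and misclassifies nothing. The next sentence plainly makes Day 9 events treatment-emergent, Protocol 8 leaves details to the SAP, and the SAP has no pretreatment table that could receive them. Most of this stands: the intent is probably sound. But Protocol 3.1 gives Day 9 that very name, no pre-treatment washout exists in the schedule, and Protocol 8.4.2 still plans pretreatment listings and SAE tabulations.

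On dates, the 86.8% concerns days on which AEs are recorded daily and, from the evening of Day 2, subjects are confined. Partial dates are least likely then. That is right, and is why the outpatient figure is given beside it. SAP 2.13 also keeps original dates with imputed ones, and says that imputation serves placement in the summary tables without saying that it decides the regimen. If first dose means Day 4, no day-missing Period 2 or 3 onset is dated before the first randomised dose, so TEAE status does not change; only placement by regimen could.

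A reader might also infer that *Day 1-2* conflicts with the three-period crossover. It does not: it conflicts with the confined days within each period, and the main clause still asks for times on all housed days. Nor can one conclude that no rule links events to regimens. SAP 2.7.2 reports hypoglycaemia by treatment received, and the table shells are in a separate file that is not available here.

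**Conclusion.** The Protocol's pretreatment definition is wrong as written. Taken literally, it gives new AEs on 9 of 12 pretreatment days two classes, including Day 9 of every period. SAP 2.13 uses an anchor that does not suit a crossover. The 86.8% and 52.3% hold only for events with the day missing, 14-day washouts, and attribution by imputed date to the most recent Day 4. The documents do not say how often dates are partial; such events are likely few.

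A reader might infer that Day 9 events will be lost from the safety tables, or that most later-period AEs will be assigned to the wrong regimen. Neither is supported. The AE tables listed in the SAP follow the TEAE rule, and the percentages do not apply to fully dated events. AE inference is not planned, and individual listings with dates would show any anomaly. The effect on results cannot be sized. Severity: minor.

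**What to change.** - **Protocol 7.2 and 8.4.2:** delete *placebo washout period* from the pretreatment definition, leaving the run-in.
- **Both documents:** define run-in and TEAE per period, with TEAE counted from that period's first randomised dose on Day 4.
- **SAP 2.13:** impute partial AE start dates relative to the period in which the event was reported.
- **Wording only:** reconcile *Day 1-2* in Protocol 7.4.1 with the confined days (evening of Day 2 to Day 10), and *washout period placebo* in Protocol 7.4 with the Day 1 run-in placebo.

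The cost is Protocol and SAP text and one AE programming rule. No visit or procedure is added. The CRF is not among the documents; if it lacks an AE time field for the confined days, one would be needed.

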7.3 Definition of Serious Adverse Event

A SAE is defined in 21 CFR 312.32(a) as follows:

An AE is considered “serious” if, in the view of either the Investigator or Sponsor, it results in any of the following outcomes:

- Death;
- Life-threatening AE;
- Inpatient hospitalization or prolongation of existing hospitalization;
- Persistent or significant incapacity or substantial disruption of the ability to conduct normal life functions;
- Congenital anomaly/birth defect.

Important medical events that may not result in death, be life-threatening, or require hospitalization may be considered serious when, based upon appropriate medical judgment, they may jeopardize the patient or subject and may require medical or surgical intervention to prevent one of the outcomes listed in this definition. Examples of such medical events include allergic bronchospasm requiring intensive treatment in an emergency room or at home, blood dyscrasias or convulsions that do not result in inpatient hospitalization, or the development of drug dependency or drug abuse.

An AE is considered “life-threatening” if, in the view of either the Investigator or Sponsor, its occurrence places the patient or subject at immediate risk of death. It does not include an AE that, had it occurred in a more severe form, might have caused death.

7.3.1 Adverse Events of Hypoglycemia

The CTCAE (version 4.0) definition for mild, moderate, and severe hypoglycemia based on blood glucose will be used, as shown below:

Mild: from 55 to <70 mg/dL (3.0 to < 3.8 mmol/L)

Moderate: from 40 to < 55 mg/dL (2.2 to < 3.0 mmol/L)

Severe: from 30 to < 40 mg/dL (1.7 to < 2.2 mmol/L)

Life Threatening: < 30 mg/dL (< 1.7 mmol/L)

7.4 Eliciting and Reporting of Adverse Events

AE monitoring will start immediately following the first dose of washout period placebo and will continue through the Follow-Up Visit. Any subject with a possible study treatment-related AE at the Follow-Up Visit will be followed until resolution or stabilization of the event. Further, any SAE, whether or not related to study treatment, that occurs within 30 days following the last dose of study treatment will be followed until resolution or stabilization of the event. This may require additional clinical assessments and laboratory tests. The follow-up results will be recorded in the subject's source documentation and in the CRF.

Subjects will be instructed to report all AEs experienced during the study, and subjects will be assessed for the occurrence of AEs throughout the study. In order to avoid bias in eliciting AEs, subjects will be asked general, non-leading questions such as "How are you feeling?"

All AEs, including pretreatment and TEAEs, reported by the subject, observed or otherwise identified by the Investigator, or other Investigational Site personnel will be documented.

Medical conditions existing at Screening should be recorded as medical history. New or worsening pre-existing medical conditions or diseases are considered AEs if they arise or worsen after the Screening visit, and should be recorded as AEs.

Surgical procedures themselves are not AEs; they are therapeutic measures for conditions that require surgery. The condition for which the surgery is required is an AE if it occurs or is detected following the first dose of Study treatment through the Follow-Up Visit. Conditions leading to planned surgical procedures are not AEs if the condition(s) was (were) known before study treatment. In the latter case, the condition should be reported as medical history.

7.4.1 Routine Reporting of Adverse Events

All AEs, whether or not associated with the study treatment, that are observed by the Investigator, other Investigational Site personnel, or those reported by the subject will be recorded in the subject's source documentation and on the AE page of the CRF. Copies of the SAE CRF pages or an SAE listing generated based on the CRF pages will be submitted to the Sponsor at regularly scheduled intervals to allow the Sponsor to meet expedited regulatory reporting requirements under 21 CFR 312.32 (see Section 7.4.2 for further detail) and regular regulatory reporting requirements under 21 CFR 312.33.

For each AE, the following information will be entered in the CRF:

- Medical diagnosis of the event in standard medical terminology (if a medical diagnosis cannot be determined, a description of each sign or symptom characterizing the event);
- Date of onset of any new AE or worsening of a previously observed AE. For the days when the subject is housed in the CRU (Day 1-2), the time (based on a 24-hour clock) of onset should be recorded if available;
- Date of resolution of the event (or confirmation ongoing). For the days when the subject is housed in the CRU (Day 1-2), the time (based on a 24-hour clock) of resolution should be recorded if available;
- Whether the event is serious (per definition in Section 7.3), and if so, the reason it is considered serious;
- Severity of AE (per definition in Section 7.6);
- Assessment of the attributability of the AE to the study treatment [per definition in Section 7.5];
- Whether the event is expected (per definition in Section 7.7);
- Action taken in treating the AE (including concomitant medications or therapies administered) and/or change in the study treatment administration or dose (including whether the study treatment was temporarily interrupted or discontinued);
- Outcome of AE (per definition in Section 7.8).

7.4.2 Reporting of Serious Adverse Events, Including Death

The Sponsor will adhere to all expedited regulatory reporting requirements as per 21 CFR 312.32.

SAEs, including death due to any cause, which occur during this study or within 30 days following the last dose of the study treatment, whether or not related to the administration of study treatment, must be reported by the Investigator or other Investigational Site personnel to the Medical Monitor by telephone or fax **within 24 hours of learning of the event**. The contact information for the Medical Monitor is provided below.

Medical Monitor:

[name]
Safety Office, Integrium, LLC
Office: [contact]
Cellular: [contact]
Email: [contact]

SAE Forms will be provided by the Sponsor or Sponsor designated CRO. If all information is not known at the time of initial reporting, an initial report should still be made. In the event there is a question as to whether the experience is serious, the information should be forwarded to the Medical Monitor for review. The Investigator is responsible for following up on completion of the SAE Form. The Investigator will submit substantiating data in hard copy form, such as

diagnostic test reports and progress notes, to the Medical Monitor. In the case of fatality, autopsy reports will be furnished to the Medical Monitor as soon as available. If the Medical Monitor is informed of a SAE via a telephone call, preliminary information will be obtained, and the study site will be instructed to fax an SAE Form.

In the event of a medical emergency or an SAE that is unexpected (as defined in Section 7.7) and possibly related to the study treatment (s) (i.e., an adverse reaction or suspected adverse reaction as defined in Section 7.5), the blind will be broken for the subject that experiences the event. An emergency code break envelope for each subject will be provided to the Investigational Site and also to the Medical Monitor. In the event that the Investigational Site personnel need to unblind the study treatment and cannot access the relevant code break envelope at the site, they can contact the Medical Monitor.

The initial SAE Form and any subsequent follow-up SAE Forms submitted to provide more accurate, corrected, or new information must be signed by the Investigator. The Investigator and Investigational Site Personnel must make every reasonable effort to obtain, from other institutions if necessary, all supporting medical case records as needed to comply with expedited Investigational New Drug application (IND) safety reporting requirements.

If the SAE involves expedited IND safety reporting (as determined by the Sponsor or designee), all supporting medical records must be submitted to the Sponsor or designee within 4 calendar days for death or life-threatening events, and 10 calendar days for all other events. In cases where medical records and supporting documentation are unobtainable, the Investigator must generate a narrative of the event utilizing, when necessary, interviews with the subject, their family members and care givers as appropriate.

The Investigator must also promptly inform the governing IRB of the SAE in accordance with the governing IRB's requirements. Any SAE that is determined by the Sponsor to be reportable to the FDA as an IND Safety Report (as defined in 21 CFR 312.32) will be reported to FDA by the Sponsor or designee within the specified time frame. All IND Safety Reports will also be promptly provided to the Investigator for submission to his/her IRB. Similarly, any SAE that is determined by the Sponsor to require expedited reporting to other regulatory authorities will be reported to the appropriate authorities by the Sponsor or designee within the specified time frames, and will be provided to the Investigator for submission to his/her IRB.

The Investigator, Medical Monitor, and Sponsor will review each SAE report and evaluate the relationship of the adverse experience to study treatment and to underlying disease. Based on this assessment, a decision will be made concerning the need for further action. The primary consideration governing further action is whether new findings affect the safety of subjects participating in the clinical trial. If the discovery of a new adverse experience related to the study treatment raises concern over the safety of continued administration of study treatment, the Sponsor will take immediate steps to notify the regulatory authorities.

Further action that may be required includes the following:

1. Alteration of existing research by modification of the protocol;
2. Discontinuation or suspension of the study;
3. Alteration of the informed consent process by modification of the existing consent form and informing current study participants of new findings;

4. Modification of previously identified expected adverse experiences to include adverse experiences newly identified as study treatment-related.

If the subject or partner of a subject participating in the study becomes pregnant during the study or within 30 days of discontinuing study medication, the Investigator should report the pregnancy to Integrium within 24 hours of being notified. Safety personnel will then forward the Exposure In Utero form to the Investigator for completion.

The subject or partner should be followed by the Investigator until completion of the pregnancy. If the pregnancy ends for any reason before the anticipated date, the Investigator should notify the Sponsor. At the completion of the pregnancy, the Investigator will document the outcome of the pregnancy. If the outcome of the pregnancy meets the criteria for immediate classification as an SAE (i.e., postpartum complication, spontaneous abortion, stillbirth, neonatal death, or congenital anomaly), the Investigator should follow the procedures for reporting an SAE.

